The NGHP planned to formally evaluate the quantitative and qualitative impact and outcomes of use of CADe within VA medical centers following the purchase and distribution to randomly selected gastrointestinal endoscopy units.

Setting:

Veteran Health Administration (VA) Medical Centers

Intervention:

As part of ongoing quality assurance efforts, the NGHP purchased 115 Medtronic GI Genius® CADe devices in late 2022. All facilities were sorted according to their facility-level ADR (for all indications) and categorized as below 30%, 30% to <40% or ≥40%. A random number generator was then used to sort the VA medical centers within each of these 3 ADR strata. Alternating facilities (i.e., approximately 50%) of facilities within the 2 lower ADR stratum were allocated the CADe devices. To assure equitable distribution of the remaining CADe devices across the 18 VA Integrated Service Networks (VISNs), the remaining devices were offered to randomly selected facilities (all within the ≥40% ADR stratum) such that each VISN had 2-3 facilities with CADe devices.

Upon identification of a potential site, the Gastroenterology Section Chief (or equivalent) at that randomly selected site was asked if they were interested in receiving the devices and if all endoscopists at their facility would agree to use the device during colonoscopy. The physicians were not mandated to use the devices but were asked to notify the NGHP if endoscopists were not routinely using the devices so that the devices could be reallocated to other VA facilities that would make use of the CADe devices. Upon receiving concurrence from facility endoscopy leadership, the devices were installed in all procedure rooms that are routinely used for colonoscopy at that facility. The devices were not installed on travel carts for emergency procedures. One facility did decline to receive the devices due to concerns that the devices would negatively impact efficiency in the endoscopy unit. That facility was replaced with another randomly selected VA medical center. Ultimately, 43 VA facilities received and installed the 115 CADe devices.

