 - a) This serves as a surrogate for false positive lesion detection during use of CADe
- 5) Withdrawal time when no maneuvers are performed
 - a) Limited to Provation Sites
 - b) To assess the negative impact of CADe on procedure time or a possible Hawthorne effect.
- 6) Provider satisfaction with CADe for colonoscopy
- 7) Adenoma detection rate stratified by the endoscopist's pre-CADe ADR quintile

Additional analyses to be considered (due to data availability):

- 1) Bowel preparation quality
 - a) Limited to Provation sites
- 2) Number of polyps per colonoscopy
 - a) Limited to Provation sites
- 3) Size of polyps detected
 - a) Limited to Provation sites
- 4) Advanced neoplasia detection rates
 - a) Limited to Provation sites
- 5) Surveillance recommendations after colonoscopy

Independent Variables:

- 1) VA Facility characteristics
 - a) Pre-randomization adenoma detection rate

- 2) Patient characteristics
 - a) Age
 - b) Gender
 - c) Race
 - d) Ethnicity
 - e) Rurality
- 3) Provider characteristics
 - a) Specialty
 - b) Sex
 - c) Years since completion of medical training
- 4) Colonoscopy indication (Provation sites only, if available)
 - a) Screening
 - b) Surveillance
 - c) FOBT+
 - d) Other
 - e) Unknown
- 5) Bowel preparation quality (Provation sites only, if available)
 - a) Adequate vs. inadequate
 - b) Aronchick
 - c) Boston Bowel Preparation Score

Statistical Methods:

Colonoscopies performed on the day of CADe installation and the next 5 colonoscopies performed by each endoscopist after the date of installation (or matched date for control sites) will be excluded as a washout period to minimize training adaptation. For the 26 endoscopists who performed colonoscopies at multiple facilities, we will retain only procedures at the facility where they performed the largest number of colonoscopies.

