Baseline data will be summarized as number (%), mean (\pm standard deviation) or median (interquartile range), as appropriate. For binary outcomes, we will estimate the association of CADe on study outcomes using mixed effects logistic regression (PROC GLIMMIX, SAS software, Cary, NC) with random intercepts for facility and endoscopist and random slopes (at the facility and endoscopist level) for study phase. We will also include fixed effects for group, phase, and a group by phase interaction (product term), with colonoscopy serving as the unit of analysis. The group by phase interaction is quantified as a ratio of odds ratios, where a coefficient greater than 1 for the interaction term (or 0 on the log-odds scale) reflects increased neoplasia detection in the post-deployment phase versus the pre-deployment phase in the CADe group compared to the non-CADe group. We will control for pre-randomization ADR stratum, patient demographics (e.g., sex, age, race, ethnicity and rurality), and endoscopist information (e.g., specialty, sex, years since medical degree) in all analyses.

After estimating the association of CADe on adenoma detection, we will assess whether the effect was moderated by patient and endoscopist characteristics. We will fit additional models

for each potential moderator, adding a main effect for the moderator and interactions (product terms) with group, phase, and group by phase terms as fixed effects.

Withdrawal time information will only be available from the subset of VA facilities that use Provation MD software. As withdrawal time is a continuous variable, we will use a linear mixed effects regression model with the same predictors as described above. We will include only those colonoscopies without an associated pathology report and where cecal intubation was complete.

To assess whether the effect of CADe on ADR is moderated by endoscopist ADR quintile, endoscopists with at least 100 colonoscopies in the pre- and post-deployment phases each will be divided into quintiles based on pre-intervention ADR. The quintile variable will be entered into the model described above as a main effect and an interaction (product term) with the group, phase, and group by phase terms.

References:

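### The ADR-quintile analysis ranks endoscopists on the same pre-phase colonoscopies it uses as outcome; the controls remove most of the regression to the mean, but a small residual against CADe stays in the lower and middle quintiles

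*Combined protocol and SAP*

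**What the plan says.** Version 2.1 lists as secondary outcome 7: "Adenoma detection rate stratified by the endoscopist's pre-CADe ADR quintile". Under Statistical Methods, only those with 100 or more procedures in both phases enter this analysis, and they are "divided into quintiles based on pre-intervention ADR". On how this classification then joins the base model, the plan writes: "The quintile variable will be entered into the model described above as a main effect and an interaction (product term". The products are taken with arm, with period and with their interaction. The base model has "random intercepts for facility and endoscopist and random slopes (at the facility and endoscopist level) for study phase". On covariates the plan says: "We will control for pre-randomization ADR stratum, patient demographics" and endoscopist information. It states no stratum-by-phase term, no separate period for ranking and no reliability correction. Control sites are given matched dates, so they have both phases.

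Allocation depended on facility ADR. Under Intervention: "Alternating facilities (i.e., approximately 50%) of facilities within the 2 lower ADR stratum were allocated the CADe devices". After that, "the remaining devices were offered to randomly selected facilities (all within the ≥40% ADR stratum"), so that each regional network had two or three CADe facilities.

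**The concern.** An endoscopist's observed pre-phase ADR is the true rate plus sampling error. Ranking on it puts people with unlucky runs in quintile 1 and people with lucky runs in quintile 5. Their post-phase rates drift back towards their true rates with no intervention. Because the ranking data are also the pre-phase outcome, this drift appears as pre-to-post change.

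A concurrent control group cancels the drift only if endoscopists in the same observed quintile come from the same distribution of true ADR in both arms. The allocation works against that. CADe sites are over-represented in the lower ADR strata, so a low-quintile control endoscopist is more often someone from a facility at or above 40% who had a poor run, and will rise further. The contrast then leans against CADe in the lower and middle quintiles, which matters for a question about effect moderation by baseline ADR.

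**Working it through.** The documents give no sample size, power or expected quintile effect, so there is no stated figure to reproduce.

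**Inputs from the documents.** 43 CADe facilities; about 50% allocation in the two lower strata; overall ADR 47%; at least 100 colonoscopies per phase; data from 1 October 2021 to 30 June 2023 (638 days). The control count, over 100, is in Version 1.1; Version 2.1 gives none.

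**Assumed.** Standard deviations, endoscopists per facility (4), volumes, 146 facilities in total, and the date dividing the phases.

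**1. Allocation imbalance.** The overall CADe share is at most 43/(43 + 101) = 29.9%. With about 50% in the lower strata, the share in the ≥40% stratum must be below about 30%. If 20% of 146 facilities lie in the lower strata, it is (43/146 - 0.5 × 0.20)/0.80 = 24%.

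**2. Likely pre-phase volume.** If the phases divide on 1 December 2022, there are 426 pre-phase and 212 post-phase days, so 100 post-phase cases at a steady rate imply 100 × 426/212 = 201 pre-phase cases. If they divide on 1 March 2023: 100 × 516/122 = 423. Values near 250 are therefore likelier than 100.

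**3. Within-quintile drift, closed form.** In percentage points, v = 100² × 0.47 × 0.53/n; R = SD²/(SD² + v); expected rise in quintile 1 = (1 - R) × 1.40 × √(SD² + v), with an equal fall in quintile 5.

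| n (pre) | v | SD 8 | SD 12 |
|---|---|---|---|
| 100 | 24.9 | 3.7 | 2.7 |
| 250 | 10.0 | 1.6 | 1.1 |
| 400 | 6.2 | 1.0 | 0.7 |

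**4. Contrast with no CADe effect.** Simulation with the stated allocation and pooled cuts. The contrast is the CADe-minus-control difference in pre-to-post change, in ADR points, for quintiles 1 to 5. SDs are on the logit scale (facility / endoscopist within facility).

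| n pre/post; SDs | Control change, Q1 and Q5 | Contrast as planned | With stratum × phase |
|---|---|---|---|
| 350/150; 0.33/0.33 | +0.89, -0.83 | -0.17, -0.17, -0.15, -0.07, -0.04 | 0.06, 0.02, -0.04, -0.01, -0.03 |
| 250/100; 0.33/0.33 | +1.25, -1.14 | -0.22, -0.26, -0.21, -0.09, -0.09 | 0.09, 0.00, -0.05, -0.02, -0.07 |
| 250/100; 0.42/0.25 | +1.25, -1.10 | -0.30, -0.52, -0.31, -0.11, -0.02 | 0.09, -0.02, -0.04, -0.03, -0.01 |
| 250/100; 0.33/0.20 | +1.53, -1.38 | -0.37, -0.49, -0.25, -0.07, -0.02 | 0.12, -0.06, -0.06, -0.02, -0.02 |
| 100/100; 0.33/0.33 | +2.95, -2.76 | -0.54, -0.57, -0.45, -0.22, -0.11 | 0.16, -0.01, -0.09, -0.02, -0.05 |
| 100/100; 0.33/0.20 | +3.52, -3.19 | -0.80, -0.92, -0.59, -0.24, -0.01 | 0.22, -0.07, -0.13, -0.08, 0.01 |

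With 146 facilities the standard errors are about 0.9 to 1.3 points in the first four rows and 1.2 to 1.5 in the last two. The bias in quintiles 1 to 3 is then about 0.15 to 0.45 SE, and 0.3 to 0.7 SE, respectively.

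**5. Why stratum adjustment does not help as planned.** A stratum main effect takes the same value in both phases, so it drops out of pre-to-post change. A generalised least squares fit on endoscopist logits, with a stratum main effect and random intercepts and phase slopes at both levels, confirms this. With SDs 0.33/0.33, the ratios of odds ratios by quintile were 0.974, 0.972, 0.982, 0.985, 1.000 at 100 pre-phase cases and 0.991, 0.989, 0.990, 0.999, 0.998 at 250. The lowest single value, with 100 cases and SDs 0.33/0.20, was 0.958. With equal allocation in every stratum, the raw ratios were 0.999 to 1.006, which identifies the cause.

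**The case against.** The strongest reply is that the plan defines its effect as the group-by-phase ratio of odds ratios and tests moderation of that ratio. It nowhere says that within-quintile change will be reported as a CADe effect. This stands. A reader might infer that the quintile results would be pure artefact, or wrong by one to four points. Those figures are within-arm changes, not the planned contrast, and the documents do not support that reading. Nor is outcome 7 framed as a question about low-ADR endoscopists alone; it covers all quintiles.

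It is also fair that the residual is below one standard error in every setting examined and that every size rests on inputs the documents do not give. The plan does not say whether cuts are pooled or made within arm. Cut within arm, the ratios were 0.995 to 1.008, so the residual nearly vanishes, but a given quintile then means a different ADR range in each arm, and the within-arm drift remains. Finally, the text does not say outright that the ranking colonoscopies are the outcome colonoscopies, though it names no other period and the pre-phase minimum of 100 points that way.

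What survives is that the imbalance in allocation is built into the design, the direction of the residual with pooled cuts is predictable, and the planned adjustment does not remove it.

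**Conclusion.** The point holds in a limited form. Pre-to-post change within a quintile cannot be read as an effect in either arm: with no CADe effect, expect roughly +1 to +2 points in quintile 1 and -1 to -2 in quintile 5, and about 3 or more each way if pre-phase volumes are near 100. The planned contrast removes most of this. With pooled cuts it keeps a bias against CADe of about -0.2 to -0.6 points in quintiles 1 to 3 (ratio of odds ratios about 0.97 to 0.99; up to -0.9 points in the least favourable setting) and close to nothing in quintile 5. Direction and incomplete cancellation follow from the stated allocation and pooled cuts; the sizes depend on the assumed SDs and volumes.

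A reader might also infer that the primary result is compromised. It is not: the primary model does not classify endoscopists by quintile. The residual alone would not produce a large quintile gradient.

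**What to change.** - State that quintile cuts are pooled across arms and which colonoscopies they use.
- Add a pre-randomization ADR stratum by phase term to the quintile model. This keeps the ratio-of-odds-ratios scale of the primary analysis. In the simulations the remaining bias was at most 0.12 points at 250 or more pre-phase cases and at most 0.22 at 100.
- As a sensitivity analysis, fit post-phase colonoscopies only, adjusting for stratum and the endoscopist's pre-phase log-odds of adenoma. The simulated version, using pre-phase ADR as the covariate, performed about equally well.
- Base conclusions on the between-group contrast. If within-quintile changes are tabulated, note that they include regression to the mean and are not CADe effects.

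The cost is two extra parameters and a slightly larger standard error: within about 4% in most settings, and about 7% in quintile 1 (1.32 to 1.41 points) when phase effects also varied between facilities and endoscopists. No new data are needed. Version 2.1 is dated September 2025 and the data end in June 2023, so the change should be labelled as made after data collection. A stratum-by-phase term does not remove the drift within each arm, so the reporting rule is still needed.
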